**Table 4. Summary of conversion to manual by Corindus CorPath device in percutaneous coronary interventions.**

Trial		Conversion to Manual
PRECISE	Pre-market trial for FDA clearance	1.2% (2/164)
PRECISION Registry*	Post-market trial	10.4% (99/948)
CORA-PCI	Post-market single site trial	8.3% (9/108)

\* Unpublished data

For a few secondary endpoints intending to quantify performance at 180 days, safety and effectiveness rates from a key publication (The Pipeline Trial) related to 180-day follow-up are presented in table 5.

**Table 5. Safety and Effectiveness data 180-day rates presented.**

Pipeline for Uncoilable or Failed Aneurysms Clinical Trial Becske et al 2013. 	N	180-day Results (%)
SAFETY		
• Ischemic stroke (perioperative) related to PED-associated thrombosis (patient later experienced delayed fatal hemorrhage after traumatic fall in rehabilitation facility)	107	2.8% (3/107)
• Ischemic stroke (delayed) secondary to major in-construct (PED) stenosis		---
• Ischemic stroke (delayed) from noncompliance with the required oral antiplatelet regimen		---
• Ipsilateral intraparenchymal hemorrhage (perioperative)		1.9% (2/107)
• Ipsilateral intraparenchymal hemorrhage (delayed) on day 14 (fatal)		---
• Rapidly fatal event possibly neurologic in origin		0.9% (1/107)
EFFECTIVENESS	N	180-day Aneurysm
• Angiographic evaluation that demonstrated complete aneurysm occlusion and absence of major stenosis at 180 days	106	
○ YES		73.6% (78/106)
○ NO		26.4% 28/106

The goal of the Pipeline trial safety analysis was to show the rate of ipsilateral stroke or neurologic death is statistically lower than 20%. The rate of complete aneurysm occlusion analysis goal was set at a threshold of 50%. The Pipeline trial demonstrates that treatment of large and giant cerebral aneurysms is feasible and effective, with a reasonable margin of safety. Patient follow-up for the trial consisted of repeat neurologic examinations at 30 and 180 days after device placement and a follow-up telephone call evaluation at 90 days. Further periodic follow-up visits were scheduled (through 5 years). Patients underwent conventional angiography and a neurologic examination at 180 days. In this study, the 180-day follow-up data imply that fewer angiographic follow-up visits are required.

Version Date: May 21, 2021

*This confidential document is the property of Corindus, Inc. and shall not be reproduced, distributed, disclosed or used without the express written consent of Corindus, Inc.*

## 6.5 Primary Analysis

The goal of the primary analysis will be to demonstrate that cerebral aneurysm coiling treated with CorPath GRX is as effective and safe as compared to the combined historical control treatments for cerebral aneurysm coiling treated with traditional manual operation.

For safety, if the upper bound of the 2-sided 95% confidence interval is less than the performance goal of 15%, we will conclude that the Corindus GRX system did not negatively impact safety.

For performance, if the lower bound of the 95% confidence interval for the proportion of successful patients is greater than the performance goal of 80%, we will conclude that the Corindus GRX system did not negatively impact performance.

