**Table 3a-3c. Rates presented pooled results from both arms from three (3) from randomized control trials.**

HELP Trial	N	Mortality	Procedural aneurysm rupture*	Thromboembolic complication*		
White et al 2008  N=499 RCT, covered vs uncovered coil  53% ruptured	499	2.2% (11/499) At discharge	3.4% (17/499)	9.8% (39/499)		

\* Article specifically called out that “some of these adverse events, especially procedural ones, did not result in permanent clinical sequelae.

MAPS Study	N	Mortality	Overall Complication Rate	Clinical Event Committee Adjudicated			Technical Success
				Rupture/re-rupture	Ischemic Stroke	Hemorrhagic Stroke*	
McDougall et al 2014  N=626 RCT, Matrix coil vs GDC coil  Ruptured 36.4% (228/626)	626	0.2% (1/626) Peri-proc  2.4% (15/626) 30 day	14.9% (93/626)	0.3% (2/626)	3.4% (21/626)	1.1% (7/626)	97.1% (608/626)

\*Article notes hemorrhagic strokes due to rupture/re-rupture are not included in Hemorrhagic Stroke summary

CERECYTE Coil Trial	N	Mortality	Overall Complication Rate	Rupture/re-rupture	Thromboembolic complication	Neuro-deterioration	Technical Success
Coley et al 2012  N=500 RCT, Cerecyte vs bare platinum coil  Ruptured 46.9% (233/500)	497	0% within 24-hr  0.4% (2/497) before discharge	12.3% (61/497)	3.6% (18/497)	5.6% (28/497)	3.0% (15/497)	97.2% (483/497)  (14 “unable to place coil”)

While Cerecyte and HELPS present overall complication rates in the 12-15% range, it was felt that the rates of stroke, rupture/re-rupture and death from the MAPS trial that were adjudicated by an independent clinical event committee were the most accurate to represent the expected rates of safety events for this trial. If we assume independence and add the individual rates, the

expected rate of safety events is 4.8% (30/626) but will be rounded to the nearest percent of 5% for sample size calculations.

The performance endpoint is similar to a technical success measure. Zang *et al* 2019 provided a literature review that included technical success. The weighted average was 97.6% for ruptured aneurysms. McDougall *et al* 2014 reported a similar overall procedural success of 97.1% (608/626) and Coley *et al* 2012 report a success of 92.7%, but this number does not include conversion to manual as our performance endpoint does.

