## 6.6 Sample Size Calculation

Assuming that the expected safety for procedures performed with the Corindus GRX system do not differ from historical performance, we set up a performance goal using the historical rate of 5% for safety and an 10% non-inferiority margin to set up a performance goal of 15% for safety. The safety hypothesis is:

$$H_0: p \geq 15\% \quad (5\% + 10\% \text{ NI margin})$$

$$H_a: p < 15\%,$$

where  $p$ =proportion of patients with a safety event.

A sample size of 96 subjects will have at least 90% power to test this safety hypothesis (PASS 14, one-sample proportion, exact test, normal approximation for power).

Assuming that the expected procedure success rate is similar to the 90% based on literature and our best estimate of possible conversion to manual procedures, we set up a performance goal using the historical rate of 90% for with a 10% non-inferiority margin to set up a goal of 80% for performance.

The performance hypothesis is:

$$H_0: p \leq 80\% \quad (90\% - 10\% \text{ NI margin})$$

$$H_a: p > 80\%,$$

*Version Date: May 21, 2021*

*This confidential document is the property of Corindus, Inc. and shall not be reproduced, distributed, disclosed or used without the express written consent of Corindus, Inc*

where  $p$ =proportion of patients with a successfully completed endovascular procedure.

A sample size of 108 subjects will have at least 80% power to test this safety hypothesis (PASS 14, one-sample proportion, exact test, normal approximation for power).

The overall trial sample size for the trial will be driven by the performance endpoint with at least 108 subjects enrolled.

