4.3 Primary Safety Endpoint

Objective: To assess safety of using CorPath GRX for robotic-assisted endovascular procedure.

Hypothesis:

$H_0: p \geq 15\% (5\% + 10\% \text{ NI margin})$

$H_a: p < 15\%,$

where p =proportion of patients with a safety event.

Endpoint: The proportion of subjects with a safety event where a safety event is intra- and peri-procedural events, including target aneurysmal rupture, vessel perforation or dissection, and thromboembolic event with neurological decline within 24 hours post-procedure or hospital discharge, whichever occurs first.

Subjects to Include: Analysis Cohort

Statistical Analysis: The proportion of subjects with a safety event as defined will be summarized along with a 2-sided Clopper Pearson Exact 95% confidence interval. If the upper bound is less than 15%, we will declare success and conclude that safety is not worse than the performance goal of 15%.

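### On a safety pass, Protocol 6.5 and SAP 3.2 prescribe a no-harm conclusion, but the test supports only an event rate below 15%, which is the plan's 5% manual rate plus a 10-point margin.

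*Protocol*

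**What the plan says.** The decision rule in Protocol 6.5 applies "if the upper bound of the 2-sided 95% confidence interval is less than the performance goal of 15" per cent, and on a pass "we will conclude that the Corindus GRX system did not negatively impact safety". SAP 3.2 repeats this. In both places the preceding paragraph gives the aim as showing robotic coiling to be equal in effectiveness and safety to historical controls treated manually, so the comparator is manual operation.

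Protocol 6.6 builds the goal from a "historical rate of 5% for safety and an 10% non-inferiority margin to set up a performance goal of 15% for safety". The 5% comes from Protocol 6.4, where the "expected rate of safety events is 4.8% (30/626") is rounded to the nearest percent.

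Other sections word the same test differently. Protocol 6.2 says the interval is meant to show that safety is non-inferior to a literature-based performance goal. SAP 4.3, which specifies the primary safety analysis, says of a pass: "we will declare success and conclude that safety is not worse than the performance goal of 15" per cent. The interval is Clopper-Pearson: "The proportion of subjects with a safety event as defined will be summarized along with a 2-sided Clopper Pearson Exact 95% confidence interval".

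**The concern.** A non-inferiority margin is an amount of worsening that the plan agrees to tolerate. Here it is 10 percentage points on a base of 5%. To say after a pass that safety was not harmed is to claim a margin of zero, which the hypothesis in Protocol 6.6 does not test.

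The sentence is pre-specified and stands in the section headed Primary Analysis, so it may well be carried into the report as the headline safety finding. The events concerned are aneurysm rupture, vessel perforation or dissection, and thromboembolic events with neurological decline. A system with a true rate moderately above the manual benchmark could pass and be reported as causing no loss of safety. Neither document says which of its two wordings governs the report.

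**Working it through.** **Inputs.** Historical rate 5%, margin 10 points, goal 15% (Protocol 6.6, SAP 3.2 and 4.3). Two-sided 95% Clopper-Pearson interval (SAP 4.3), which is a one-sided 2.5% test. Safety sample size 96 for at least 90% power; overall size at least 108, with up to 120 enrolled (Protocol 6.6 and 4.1).

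**1. The plan's own figure.** By the normal approximation that the plan names,

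n = [(z₀.₉₇₅·√(0.15·0.85) + z₀.₉₀·√(0.05·0.95)) / 0.10]² = [(1.960·0.3571 + 1.282·0.2179) / 0.10]² = 95.9, so 96.

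Power at n = 96 is 90.05%, so the stated figure reproduces. The exact rule at n = 96 passes up to 7 events and has 89.2% power. At n = 108 exact power is 90.8%. The sample size is not in question.

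**2. What rejecting the null shows.** The null is p ≥ 15%, so rejection shows p < 15%. Relative to the benchmark, 15% / 5% = 3 and 15% − 5% = 10 points. All rates from 5% up to 15% lie inside the alternative hypothesis, although each is worse than the benchmark.

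**3. Which results pass.** The rule is that the upper Clopper-Pearson limit lies below 15%.

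| Analysed | Events | Rate | 95% CI | Result |
|---|---|---|---|---|
| 108 | 8 | 7.4% | 3.3% to 14.1% | pass |
| 108 | 9 | 8.3% | 3.9% to 15.2% | fail |
| 120 | 10 | 8.3% | 4.1% to 14.8% | pass |
| 120 | 11 | 9.2% | 4.7% to 15.8% | fail |

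With 6 to 8 events in 108 (6/108 = 5.6% to 8/108 = 7.4%) the observed rate exceeds the benchmark, and the prescribed conclusion is still no harm.

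**4. How often a given true rate passes.** This is the exact binomial P(X ≤ 8) for n = 108 and P(X ≤ 10) for n = 120. The second column assumes that all 120 enrolled are analysed. The plan enrols up to 120 to obtain 108, and the SAP 4.1 cohort needs a recorded robotic microcatheter insertion time.

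| True rate | n = 108 | n = 120 (assumption) |
|---|---|---|
| 5% | 90.8% | 96.2% |
| 7.5% (1.5 times benchmark) | 57.8% | 71.1% |
| 8% | 50.0% | 63.5% |
| 10% (twice benchmark) | 23.6% | 33.6% |
| 12% | 8.7% | 13.4% |
| 15% | 1.3% | 2.2% |

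**5. The wordings side by side.** In the Protocol, 6.2 refers to a performance goal, while the conclusion in 6.5 refers to absence of harm. In the SAP, the conclusion in 4.3 refers to the 15% goal, while that in 3.2 refers to absence of harm. Step 2 supports the goal-based wording in each pair and not the other.

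**The case against.** The strongest reply is that this is non-inferiority shorthand which misleads nobody. The study is labelled non-inferiority throughout, the 15% goal stands in the same sentence, the sum of 5% and 10 points is printed in both documents, and the section that specifies the SAP's safety analysis already concludes correctly. The observed rate and its interval will be reported in any case. All of this is true and limits the harm, but it does not make the sentence correct: the conclusion names neither goal nor margin, and a reported interval does not amend a pre-specified statement that says something else.

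Second, the pass probabilities describe the width of the margin and would be the same after any rewording. That stands. They show when the conclusion would be false; they do not measure an effect of the wording on the decision.

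A reader might also infer more than the documents support:

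- *That the Protocol and SAP contradict each other.* They share the loose sentence, and each has goal-based wording elsewhere. The inconsistency lies within each document.
- *That a rate near three times the benchmark would be reported as harmless.* A true 15% passes 1.3% of the time at n = 108, and a true 10% fails 76% of the time. The loss that could realistically be missed is about 1.5 to 2 times the benchmark.
- *That a passing trial could have shown harm.* The largest passing results, 8/108 and 10/120, have intervals that include 5%, so no pass at these sizes would show a rate statistically above the benchmark. Failing to show harm is still not showing its absence.
- *That the test or sample size is wrong.* The test is a valid test of p < 15%, and the sample size reproduces.

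**Conclusion.** The point holds as a defect in the stated conclusion, not in the analysis. Protocol 6.5 and SAP 3.2 prescribe a claim of no harm relative to manual operation that an upper limit below 15% cannot support. At 108 analysed, the claim would be made with a probability of 58% at a true rate of 7.5% and 24% at 10%. If all 120 enrolled were analysed, these would be 71% and 34%.

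The figures take the plan's 5% as the manual rate and use the exact rule of SAP 4.3. No estimate, interval or pass/fail decision is affected; what is affected is what the trial may say after a pass. The performance sentence in the same sections has the same form but is outside this point.

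**What to change.** In Protocol 6.5 and SAP 3.2, replace the safety conclusion with one that carries the meaning of SAP 4.3, for example: *on a pass, safety is concluded to be no worse than the 15% goal, that is, non-inferior to the 5% historical rate within a margin of 10 percentage points*. In the same sections, qualify the safety half of the goal sentence in the same way; otherwise it still promises equality with manual treatment. Wherever the safety result is presented, show the 5% benchmark beside the observed rate and 95% interval, which are already planned.

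Leave the goal, margin, test and sample size unchanged.

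The cost is two sentences edited in each document and one reference figure added to the safety table. No data or subjects are needed. The downside for the sponsor is a less favourable claim on a pass.

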### 6.1 Analysis of Primary Effectiveness Endpoint

The primary effectiveness endpoint will be defined as successful completion of the robotic-assisted endovascular procedure absent any unplanned conversion to manual operation for guidewire, microcatheter, embolization coil(s), intracranial stent(s), or inability to navigate vessel anatomy. The proportion of subjects with a successfully completed endovascular procedure will be summarized along with a 2-sided 95% exact binomial confidence interval to demonstrate that the effectiveness is not inferior to a performance goal based upon historical rates from recent literature for comparable procedures.

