For the conversion to manual aspect, there are not data available for treatment of intracranial aneurysms, but we can look at past Corindus CorPath performance for PCI. In Table 4 below, the premarket trial results 1.2% for unplanned conversions, but the rate was considerably higher in the real-world post-market trial with 10.4% unplanned conversions.

To estimate the overall rate of success for the performance endpoint, we will use the highest rate of 10.4% rounded to the nearest percent of 10%, or in terms of success, 90% expected performance success rate.

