4.2 Primary Effectiveness Endpoint

Objective: To assess effectiveness of using CorPath GRX for robotic-assisted endovascular procedure.

Hypothesis:

$H_0: p \leq 80\% \text{ (90\% - 10\% NI margin)}$

$H_a: p > 80\%,$

where p =proportion of patients with a successfully completed endovascular procedure.

Endpoint: The proportion of subjects with successful completion of the robotic-assisted endovascular procedure absent any unplanned conversion to manual for guidewire or microcatheter navigation, embolization coil(s) or intracranial stent(s) deployment, or an inability to navigate vessel anatomy.

Subjects to Include: Analysis Cohort

Statistical Analysis: The proportion of subjects with a successful procedure completion as defined will be summarized along with a 2-sided Clopper Pearson Exact 95% confidence interval. If the lower bound is greater than 80%, we will declare success and conclude that effectiveness is not inferior to the performance goal of 80%.

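### A pass on the effectiveness endpoint is worded as no harm relative to manual coiling, but the 80% goal is built only from the robot's own coronary conversion rate and a 10-point margin

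*Protocol*

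**What the plan says.** **Aim and conclusion.** Protocol 6.5, repeated in SAP 3.2, sets out to show that CorPath coiling is "as effective and safe as compared to the combined historical control treatments for cerebral aneurysm coiling treated with traditional manual operation". For effectiveness, if the lower limit of the 95% interval exceeds 80%, "we will conclude that the Corindus GRX system did not negatively impact performance".

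**Narrower conclusion elsewhere.** On the same test, SAP 4.2 will "conclude that effectiveness is not inferior to the performance goal of 80" per cent. Protocol 6.1 likewise speaks of showing that effectiveness is "not inferior to a performance goal based upon historical rates from recent literature for comparable procedures".

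**Source of the goal.** Protocol 6.4 and SAP 3.1 first cite technical success in coiling studies (97.6% in a literature review of ruptured aneurysms, 97.1% in a randomised coil trial). They add that this kind of figure leaves out conversion to manual, which the trial's endpoint counts. On conversion, "there are not data available for treatment of intracranial aneurysms, but we can look at past Corindus CorPath performance for PCI". Of three CorPath coronary series, "we will use the highest rate of 10.4% rounded to the nearest percent of 10" per cent. That series is the post-market registry (99/948), footnoted in Table 4 as "Unpublished data".

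**Label.** Protocol 6.6 and SAP 3.2 describe the expected rate as resting on literature and "our best estimate of possible conversion to manual procedures, we set up a performance goal using the historical rate of 90" per cent, less 10 points. The Study Objective in the Protocol's Study Summary describes the criteria as applying to manual operation and drawn from the scientific literature.

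**The concern.** To say that a system did not harm performance is to make a comparison. The sentence itself names no comparator, but the opening paragraph of Protocol 6.5 and SAP 3.2 supplies one: historical manual coiling. If the threshold contains no manual rate, exceeding it says nothing about that comparison.

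What is at stake is the trial's primary effectiveness claim. As written, a pass would license a statement about robotic against manual coiling that the test cannot support. A report could take that statement from SAP 3.2 or the narrower one from SAP 4.2, and cite the plan either way.

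**Working it through.** **1. Rebuild the goal (Protocol 6.4 and 6.6, Table 4).**
- Conversion: 99/948 = 10.44%, rounded to 10%.
- Expected success: 1 − 99/948 = 89.56%, taken as 90%.
- Goal: 90% − 10 points = 80%.

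Does a manual rate enter anywhere? If technical success had been multiplied in, the expected rate would be 0.971 × 849/948 = 87.0% or 0.976 × 849/948 = 87.4%. Neither is 90%. The coiling figures are background; the arithmetic uses only the registry and the margin.

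**2. Reproduce the sample size.** Inputs: null 80%, true rate 90%, one-sided 0.025 (two-sided 95% interval), 80% power.

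n = [(1.960 × √(0.8 × 0.2) + 0.842 × √(0.9 × 0.1)) / 0.10]² = 107.4, so 108, as stated.

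Power by the normal approximation is 80.3%. Exact power at n = 108 and a true rate of 90% is 81.0%. The plan's figure is sound.

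**3. The pass rule (Clopper-Pearson 95% lower limit above 80%).**

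| n | Successes | Lower limit | Result |
|---|---|---|---|
| 108 | 94 | 79.21% | fail |
| 108 | 95 | 80.30% | pass |
| 120 | 104 | 79.25% | fail |
| 120 | 105 | 80.22% | pass |

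The smallest pass at n = 108 is 95/108 = 88.0%, leaving 13 subjects (12.0%) who did not meet the endpoint. At n = 120 it leaves 15 (12.5%). These counts follow from any 80% goal at these sizes. They show what a pass establishes, not that the goal is wrong.

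**4. How far the goal rests on robotic coronary data.** Keep the 10-point margin and change only the Table 4 row:

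| Series | Success | Less 10 points | Rule at n = 108 |
|---|---|---|---|
| 99/948 | 89.6% | 79.6% | 95 |
| 9/108 | 91.7% | 81.7% | 97 |
| 2/164 | 98.8% | 88.8% | 103 |

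For a given margin, the goal moves with the choice of CorPath coronary series. No row tells the reader anything about manual coiling. This is an illustration, not a proposal to change the goal.

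**5. The two conclusions side by side.** Protocol 6.5 and SAP 3.2 conclude no negative impact, under an aim that names manual operation. Protocol 6.1 and SAP 4.2 tie the conclusion to the performance goal. Goal, interval and pass rule are identical, so the decision is the same; only the claim attached to it differs.

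**6. Source labels for effectiveness.** The Study Summary objective (manual operation), Protocol 6.1 (recent literature, comparable procedures) and Protocol 6.6 with SAP 3.2 (literature, historical rate) do not describe an unpublished registry of the same robot in another vascular bed.

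**The case against.** The strongest defence is that the plan is open about all this. Protocol 6.4 and SAP 3.1 state that no aneurysm data on conversion exist, name the coronary source, footnote it as unpublished, and explain why technical success in coiling studies is not the same measure. A fixed performance goal is a legitimate single-arm design, and the sections that define the analysis, Protocol 6.1 and SAP 4.2, already limit the inference to that goal. The broad wording sits in Protocol 6.5 and in a sample-size section of the SAP.

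This stands as far as it goes. The derivation is not hidden, and the plan did consider coiling rates. But disclosing a derivation does not correct a conclusion drawn beyond it. The plan's own reason for setting those rates aside, that they omit conversion, is also the reason the endpoint cannot be compared with manual operation.

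It could also be said that taking the highest conversion rate is cautious. It is cautious for power; it also gives the lowest goal of the three series.

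Two stronger readings are tempting:
- A reader might set 80% against 97.1% or 97.6% and infer that the goal tolerates a robot some 17 points worse than manual. The documents do not support this, because the two measures count different things.
- A reader might infer that every reference to historical controls or scientific literature is wrong. Protocol 1.2 and 3.1, the SAP's introductory text and the opening of SAP 4 are overview sentences covering safety and effectiveness together. They fit the safety goal, whose 5% comes from a published coil trial, and need no change.

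**Conclusion.** The concern holds as a fault of inference and labelling. A pass supports the statement that robotic completion without unplanned conversion exceeds 80%. It does not support absence of negative impact relative to manual coiling, because no manual rate enters the goal and the endpoint has no like-for-like manual counterpart. The plan also attaches two conclusions to one test, and misdescribes the source of the 90% in the Study Summary objective, Protocol 6.1, Protocol 6.6 and SAP 3.2.

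No design figure is affected: the rule stays at 95/108 or 105/120, and exact power is 81.0% at n = 108 if the true rate is 90%. A reader might infer that the sample size is wrong or that the two SAP sections could give different pass/fail results; neither follows.

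The verdict rests on reading the conclusion together with the aim stated at the head of the same section. The conclusion sentence alone does not mention manual operation.

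**What to change.** **(a) One conclusion.** In Protocol 6.5 and SAP 3.2, replace the effectiveness conclusion with: robotic completion without unplanned conversion exceeds the 80% performance goal. Use the same sentence in SAP 4.2. In the aim at the head of Protocol 6.5 and SAP 3.2, limit the comparison with manual operation to safety.

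**(b) Accurate source.** In Protocol 6.6 and SAP 3.2, relabel the 90% as an assumed rate, from unplanned conversion in an unpublished robotic PCI registry (99/948). In Protocol 6.6, SAP 3.2 and SAP 4.2, state that the 10-point margin is taken from that assumed rate and not from a manual control. Correct the source description for effectiveness in the Study Summary objective and Protocol 6.1.

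**Cost.** Goal, test, sample size and power statement are unchanged. The sponsor accepts a narrower effectiveness claim. The Protocol wording needs an amendment with the sponsor, Ethics Committee and Competent Authority approvals set out in Protocol 8.4.
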